RATIONALE	The overall goal of this project is to develop initial human data on effects of novel compounds on safety (interactions with cocaine) and efficacy (subjective response to cocaine and self administration data) in non-treatment seeking cocaine use disorder subjects. The compound to be studied will be the 5-HT ₂ CR agonist lorcaserin. Lorcaserin and other 5-HT ₂ CR agonists have been shown to reduce cocaine self-administration and cue reactivity in rodents (Cunningham et al., 2011; Manvich et al., 2012). In addition there is human safety data in non-cocaine using subjects for lorcaserin as it is currently FDA approved for obesity, and safety data from a cocaine interaction study in rodents (included below), but there is no human cocaine interaction/PK data and no PD data to support potential dosages for phase II clinical trials.
STUDY DESIGN	This is a randomized, double-blind, placebo-controlled phase 1b/2a study.
PRIMARY OBJECTIVE	1. Assess interaction between lorcaserin and cocaine in healthy cocaine using subjects. 2. Assess effects of lorcaserin on cocaine self-administration in healthy cocaine using subjects. 3. Assess effect of lorcaserin on subjective response to cocaine in healthy cocaine using subjects. 4. Assess effect of lorcaserin on cocaine PK in healthy cocaine using subjects.
SECONDARY OBJECTIVES	Assess effect of lorcaserin on response inhibition in healthy cocaine using subjects.
NUMBER OF SUBJECTS	18
SUBJECT SELECTION CRITERIA	Inclusion Criteria: In order to participate in this study, subjects must: 1. Males and females between 18 and 59 years-of-age. 2. Understand the study procedures and provide written informed consent. 3. Meet current DSM-5 criteria for cocaine use disorder, at least moderate severity, and current DSM-IV diagnosis of cocaine dependence, but are not seeking treatment. 4. Currently using cocaine by smoking or intravenous route of administration as determined by self-report and have a positive urine

- drug screen for cocaine during screening.
5. Have vital signs as follows: resting pulse below 95 bpm, blood pressures below 140 mm Hg systolic and 90 mm Hg diastolic.
 6. Have no clinically significant abnormalities in the judgment of the study physician in hematology and chemistry laboratory tests including liver function tests.
 7. Have sinus rhythm with normal conduction (including QTcF less than 440 ms) by ECG.

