	
cohorts and presented as summary statistics.
 
2. Cocaine Self-administration: Repeated measures ANOVA with cocaine dose (0mg, 25mg) and lorcaserin dose (0mg, 10mg, 20mg) as within subject factors will be used to examine differences in mean cocaine choice selection. In addition, a Bayesian analysis will be carried out as described below.
 
3. Subjective response to cocaine: Subjective response measures (VAS) obtained during saline infusions will be compared between lorcaserin and placebo subjects to those during cocaine infusions by cocaine dose level to determine the extent to which these measures are modified by the administration of lorcaserin using repeated measures ANOVA.
 
4. Cocaine PK: Plasma concentration-time profiles of cocaine after cocaine infusion during placebo administration (Day 2) will be analyzed to obtain pharmacokinetic parameter estimates of cocaine (Tmax, AUC, apparent t_{1/2}, CL) by individual. These parameters will be compared within subjects on sessions with lorcaserin (Days 6 and 10).
 
Secondary Outcome Measure: Response inhibition: Commission errors on the IMT will be compared between lorcaserin and placebo subjects to determine the extent to which this measure is modified by the administration of lorcaserin using repeated measures ANOVA.

Planned Interim Analyses	
When approximately 50% of patients have completed the study, an interim analysis for safety will be conducted by the DSMB. Serious adverse events will be monitored by the committee on an ongoing basis throughout the study.

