Risks of Lorcaserin Administration

Lorcaserin is FDA approved for the treatment of obesity. According to the FDA briefing document on lorcaserin based on the clinical trials in patients with obesity, “the most common adverse events with an incidence in the lorcaserin group that clearly exceeded placebo were headache (16.8 vs. 10.1%), dizziness (8.5 vs. 3.8%), nausea (8.3 vs. 5.3%), fatigue (7.2 vs. 3.6%), and dry mouth (5.3 vs. 2.3%). These events were typically dose-related, mild or moderate in severity and transient. Furthermore, the excess over placebo occurred primarily within the first several days of treatment for headache and dizziness. Rates of discontinuation for adverse events were similar for lorcaserin 10 mg BID (8.6%), 10 mg QD (7.5%), and placebo (6.8%). Serious adverse events were as expected for the population, and similar in both character and frequency in the lorcaserin and placebo populations.” Because lorcaserin has the potential to impair cognitive function, patients should be cautioned about operating hazardous machinery, including automobiles, until they are reasonably certain that lorcaserin therapy does not affect them adversely. In preclinical studies abnormalities in thyroid function and liver tests have been seen in animals, but no changes in thyroid function or liver function have been noted in humans. In patients with diabetes, a drop in blood sugar has been seen. Weight loss may increase the risk of hypoglycemia in patients with type 2 diabetes mellitus treated with insulin and/or insulin secretagogues (e.g., sulfonylureas); hypoglycemia was observed in clinical trials with lorcaserin. Lorcaserin has not been studied in combination with insulin. In other populations, lorcaserin has been associated with a modest increase in blood pressure.

Other Potential Risks of Lorcaserin but not seen in Clinical Trials

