The identification of effective treatments for cocaine dependence would be a great benefit to society.

If any Psychiatric or non-Psychiatric medical illness (other than substance abuse) is discovered during the study, subjects will be referred for additional treatment in the community.

STUDY OBJECTIVES

Primary Objective

The primary objectives are to provide safety and PK information on drug interactions between lorcaserin and cocaine in subjects with cocaine use disorder, to provide information on effects of lorcaserin on subjective response to cocaine and cocaine self-administration in subjects with cocaine use disorder, and to provide safety, PK information, and cocaine self-administration and subjective response to cocaine information for compounds chosen based on results of current project and discussions with NIDA program staff.

Secondary Objectives

The secondary objective is to examine effects of lorcaserin on behavioral laboratory measures of impulsivity in cocaine dependent subjects.

STUDY DESIGN

Study Overview

The overall goal of this project is to develop initial human data on effects of novel compounds on safety (interactions with cocaine) and efficacy (subjective response to cocaine and self-administration data) in non-treatment seeking cocaine use disorder subjects. This project will provide innovative data on effects of novel compounds on cocaine self-administration in addition to needed safety data on drug interactions with cocaine. This is a Phase I human drug interaction study examining the safety of concurrent administration of cocaine

with novel compounds, and the effects of the novel compounds on subjective response to cocaine and cocaine self-administration in non-treatment seeking cocaine use disorder subjects. This data will provide important information for go/no-go decisions on phase II clinical trials using medications as a tool to enhance abstinence. The initial compound to be studied will be the 5-HT_{2C}R agonist lorcaserin, which has been shown to reduce cocaine self-administration and cue reactivity in rodents. In addition there is human safety data in non-cocaine using subjects for lorcaserin as it is currently FDA approved for obesity, but there is no human cocaine interaction/PK data and no PD data to support potential dosages for phase II clinical trials.

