Each pill bottle of study drug will be labeled with the required FDA warning statement, the protocol number, a treatment number, the name of the study physician, and directions for patient use and storage.

Administration of Study Drug

Dosage/Dosage Regimen

If subjects meet inclusion criteria, they will be seen both in the hospital and at IDAS clinic for a total of 12 active study days and monitoring procedures will be in place to detect drug and alcohol use and assess for adverse events at each visit. In addition, the hospital cocaine administration procedures will reduce the likelihood of increased cocaine craving after cocaine administration. Subjects will undergo procedures as described below. Subjects will not be allowed to smoke cigarettes, as smoking is not allowed in the hospital or anywhere on the VCU campus. Subjects will have the option to use a nicotine patch dosed based on the amount of daily cigarettes smoked. Subjects will not be allowed to leave the CRS Unit nor receive visitors during their study visits. Subjects who are unable to comply with these restrictions will be dropped from the study. After a screening cocaine infusion to determine safety, eligible subjects will be randomized to Group A –placebo only or Group B –placebo followed by an ascending dose of lorcaserin. Six subjects will be assigned to Group A (placebo) and 12 subjects will be assigned to Group B (active lorcaserin).

Study Drug Dosage: Lorcaserin will be 10mg once daily increasing to 10mg twice daily.

Outcome Measures: The primary outcome measures are adverse events, cardiovascular responses (Heart rate (HR), blood pressure (BP), ECG measurements, subjective response to cocaine, cocaine self-administration, and cocaine blood PK. Secondary outcome measures will be impulsivity as measured by the immediate memory task (IMT).

- 1) Days 1-2: All subjects will be seen on the CRSU. All subjects will receive placebo on days 1-2 in a single blind fashion. Vital signs including heart rate, blood pressure and respiration rate will be obtained after placebo administration. Days 1-2 will be single-blind placebo, whereas all remaining study days will be double-blind. All subjects will leave the CRSU at the end of each study day.

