Children as defined by NIH (age 18-21 years) will be included in this research. The incidence of severe cocaine abuse/dependence is relatively small in the population of youth less than 18 years old. From a safety perspective, risks of exposure to the proposed study medication and cocaine administration in substance-dependent children under 18 have not been established.

Analysis of Primary Endpoint

1. Safety: Heart rate (HR) and blood pressure (BP) measures during saline infusions will be compared to HR and BP after each cocaine infusion (20 mg and 40 mg doses). Changes in HR and BP induced by cocaine infusion along with lorcaserin will be compared to those without lorcaserin, by cocaine dose level (20 mg and 40 mg doses), using repeated measures analysis of variance (ANOVA). Changes in ECG readings during saline infusion as compared to those taken during cocaine infusions will be reported as summary statistics. Adverse event data will be compiled for lorcaserin and placebo cohorts and presented as summary statistics.
2. Cocaine Self-administration: Repeated measures ANOVA with cocaine dose (0mg, 25mg) and lorcaserin dose (0mg, 10mg, 20mg) as within subject factors will be used to examine differences in mean cocaine choice selection. In addition, a Bayesian analysis will be carried out as described below.
3. Subjective response to cocaine: Subjective response measures (VAS) obtained during saline infusions will be compared between lorcaserin and placebo subjects to those during cocaine infusions by cocaine dose level to determine the extent to which these measures are modified by the administration of lorcaserin using repeated measures ANOVA.
4. Cocaine PK: Plasma concentration-time profiles of cocaine after cocaine infusion during placebo administration (Day 2) will be analyzed to obtain pharmacokinetic parameter estimates of cocaine (Tmax, AUC, apparent t_{1/2}, CL) by individual. These parameters will be compared within subjects on sessions with lorcaserin (Day 6 and 10).

Analysis of Secondary Endpoints

Response inhibition: Commission errors on the IMT will be compared between lorcaserin and placebo subjects to determine the extent to which this measure is modified by the administration of lorcaserin using repeated measures ANOVA.

Safety and tolerability data will be summarized by treatment group.

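### IMT commission errors alone cannot show an effect on response inhibition; correct detections, discriminability and response bias should be analysed and reported beside them

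*Combined protocol and SAP*

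**What the plan says.** The synopsis sets the secondary objective as "Assess effect of lorcaserin on response inhibition in healthy cocaine using subjects". The Secondary Objectives section words it more broadly: "The secondary objective is to examine effects of lorcaserin on behavioral laboratory measures of impulsivity in cocaine dependent subjects". Under Dosage/Dosage Regimen the instrument is narrowed to one task: "Secondary outcome measures will be impulsivity as measured by the immediate memory task (IMT").

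The endpoint itself, labelled response inhibition, is the same wherever it appears (Synopsis under Efficacy Evaluations and under Statistics, Secondary Efficacy Endpoints, Analysis of Secondary Endpoints): "Commission errors on the IMT will be compared between lorcaserin and placebo subjects to determine the extent to which this measure is modified", by repeated measures ANOVA. No section names correct detections, omissions, reaction time, discriminability or response bias as an IMT outcome or covariate. The Stroop and XY Go-No Go tasks are described in detail. The IMT is not described at all.

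Appendix 1 places the IMT on Days 1, 4, 7 and 10. On the effects of the drug, Risks of Lorcaserin Administration states: "Because lorcaserin has the potential to impair cognitive function, patients should be cautioned about operating hazardous machinery". The same paragraph gives adverse event rates from the obesity trials, lorcaserin against placebo: fatigue 7.2% against 3.6%, dizziness 8.5% against 3.8%. It calls these events typically dose-related, mild or moderate, and transient.

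**The concern.** A commission-error count mixes three things: how readily the subject responds at all, how well the subject tells targets from non-targets, and how well the subject withholds a wrong response. The label on the endpoint refers only to the third. The protocol gives its own reasons to think that lorcaserin may act on the first two.

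If lorcaserin made subjects respond less, commission errors would fall and the result could be taken as better impulse control. If it impaired memory or attention, commission errors would rise and the result could be taken as more impulsivity. As planned, nothing analysed beside the count would tell a reader which explanation applies. This is the sole secondary endpoint, and the Study Overview says the data will inform go/no-go decisions on phase II trials.

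**Working it through.** The documents give no IMT error rate, SD, effect size or power, so there is no figure of the plan's to reproduce. The check is therefore in two parts: whether anything else in the plan separates the explanations, and how the count behaves under assumed rates.

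**Does the plan already cover this?**
- The covariate rule under Data Sets Analyzed deals with baseline differences between groups. Slowing or memory change on treatment is not a baseline difference.
- The Stroop and XY Go-No Go tasks are given on Day 12 only. They have no baseline, no administration during dosing and no stated analysis.
- Adverse events are recorded daily and tabulated by group. That would show reported fatigue, but not its effect on task responding.

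**How the count moves (illustration).** Every rate here is an assumption. Write H for the proportion of targets correctly detected and F for the proportion of non-targets responded to (commission errors). Under the equal-variance detection model, d' = z(H) − z(F) is discriminability and c = −[z(H) + z(F)]/2 is response bias. Start from H = 80%, F = 30%, which gives d' = 1.37, c = −0.16 and F/H = 0.375.

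| Change, with nothing else altered | F | H | F/H |
|---|---|---|---|
| None | 30% | 80% | 0.375 |
| 10% of all responses omitted at random | 27% | 72% | 0.375 |
| 20% of all responses omitted at random | 24% | 64% | 0.375 |
| More cautious criterion (c + 0.25) | 22% | 72% | 0.303 |
| Poorer discrimination (d' − 0.25) | 35% | 76% | 0.452 |
| Poorer discrimination (d' − 0.50) | 39% | 72% | 0.542 |

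Over assumed baselines of 85/20, 80/30 and 75/35 (H/F), a criterion shift of +0.25 lowers F by 6 to 9 percentage points, and a d' loss of 0.50 raises it by 8 to 10 points. So F moves either way. H falls in every row, so H alone does not identify the cause. H and F together, through d' and c, separate a discrimination loss from a shift in responding.

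**Is the commission-to-hit ratio a remedy?** It is constant only when responses are lost evenly. Under the detection model with c = 0, F = Φ(−d'/2) and H = Φ(d'/2):
- d' = 1.5: F = 0.227, H = 0.773, F/H = 0.293.
- d' = 1.25: F = 0.266, H = 0.734, F/H = 0.362. F is up 17%, the ratio up 24%.
- d' = 1.0: F = 0.309, H = 0.691, F/H = 0.446. F is up 36%, the ratio up 52%.

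The ratio amplifies a loss of discrimination. Under the criterion shift of +0.25 it still falls by about 15% to 25% across the three baselines (0.375 to 0.303 at 80/30, or 19%).

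**What precision is available?** With 6 placebo and 12 lorcaserin subjects the standard error of a difference is SD × √(1/6 + 1/12) = 0.50 SD. With t(16) = 2.12, the 95% confidence interval is about ±1.06 SD. At an assumed two-sided 5% level, the difference detectable with 80% power is about 1.5 SD. A rule that requires no significant change in hits would therefore be met by many real changes in hits.

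**The case against.** The strongest objection is that the argument depends on a task the documents do not describe. There is no stimulus, response rule or scored output for the IMT. The memory route rests on the task's name, and the availability of correct detections is an assumption. The protocol also promises a detailed SAP before the final analysis, which might define the scoring. The first two points stand and limit the claim: no size can be given. The third does not remove the gap, because the current text names one index in every place and the promised document is not available to check.

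A reader might infer that fatigue would produce a spurious fall of 10% to 25% in commission errors. The documents do not support that. The excess fatigue is 7.2 − 3.6 = 3.6 percentage points, or 0.036 × 12 = 0.4 of a subject in the lorcaserin arm. If every excess case stopped responding altogether, the arm mean would fall by 3.6%. Adding the dizziness excess (8.5 − 3.8 = 4.7 points) with no overlap gives 8.3%. The Low and Medium labels for 10% and 25% in the power table belong to a sample size based on cocaine self-administration and say nothing about the IMT. The firmer ground is the statement on cognitive impairment, to which the protocol attaches no size.

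A reader might also infer that the plan would report sedation as a benefit. It states no direction of benefit and no success criterion for the IMT. It asks only how far the measure is modified, and that question the randomised comparison answers validly.

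**Conclusion.** The point holds as a limit on interpretation. The between-group comparison of commission errors is sound as a comparison of that count. Reading it as an effect on response inhibition is not supported by the count alone, because overall responding and discrimination also move it and the protocol itself says lorcaserin may affect cognition. Neither the baseline-covariate rule nor the Day 12 tasks fill the gap.

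The size of any distortion is unknown. The movement from 30% down to 22% or up to 39% illustrates direction on assumed rates and does not estimate what this trial would see. The conclusion rests on the ordinary meaning of a commission error and, for the memory route, on the IMT being a memory-based discrimination task as its name implies. It is a cheap improvement to one secondary endpoint and does not bear on the primary analyses or the sample size.

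**What to change.** Keep commission errors as the secondary endpoint. In the synopsis, Secondary Efficacy Endpoints, Analysis of Secondary Endpoints and the promised SAP, add that:

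1. Correct detections from the same IMT runs are analysed in the same repeated measures ANOVA and reported with commission errors.
2. Discriminability and response bias, derived from both, are analysed and reported in the same way.
3. A change in commission errors is interpreted as response inhibition only in the light of those estimates and their confidence intervals. No test of no significant change in hits should serve as the gate, since 6 against 12 subjects cannot establish it.

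Do not replace the endpoint with the commission-to-hit ratio, for the reasons shown in the working. A short description of the IMT and its scoring should be added, since the protocol has none.

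The cost is a wording change and a few more secondary estimates, which will be imprecise. No subjects, visits or procedures are added, provided that the task software logs correct detections. That should be confirmed before the text is changed.
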